5. SAMPLE SIZE AND POWER CONSIDERATIONS

Efficacy objectives:

Sample size and power consideration for the aQIV efficacy objective is based on criteria for demonstrating efficacy in placebo controlled studies provided in CBER guidance, specifically that the study should be powered to assess the lower bound of the two-sided 95% CI of vaccine effectiveness, anticipated to be substantially above zero. This study is planned using a group sequential design. The power of Cox Regression which is planned to be used for analysis is dependent on the overall number of influenza cases, so the sample sizes on number of subjects described in this section is provided more for operational reasons. Additional information on the planning of number of subjects that may need to be enrolled if it is decided to continue enrolment after interim analyses is described in [Section 8.6](#).

For the primary efficacy objective: with 1-sided alpha of 2.5% and assuming an attack rate of influenza of 3.5% among subjects enrolled in the non-influenza comparator group and 1.4% among the aQIV group, i.e. 60% assumed vaccine efficacy for aQIV, 238 events (i.e. 4,860 subjects per group under the assumed ERs) are needed with 86.5% power to show the absolute efficacy of aQIV versus non-influenza comparator, in preventing first occurrence RT-PCR-confirmed influenza A and/or B, due to any strain of influenza regardless of antigenic match to the strains in aQIV, in subjects ≥ 65 years of age, using a margin of 40% for lower bound of the CI for absolute vaccine efficacy.

For the first secondary efficacy objective: with a group vaccine efficacy of 65% but expecting conservatively reduced event rates of influenza cases due to matched strains of 2.5% among subjects in the non-influenza comparator group and 0.9% among the aQIV group then 144 events has estimated power approximately 88.5% to show the absolute efficacy of aQIV versus non-influenza comparator, using a margin of 40% for lower bound of the CI.

Assuming a drop-out rate of 10%, approximately 10,692 subjects ≥ 65 years, 5,346 per vaccine group will be randomized to receive either aQIV or non-influenza comparator (Boostrix®) in a 1:1 allocation ratio, stratifying by age (≥ 65 to 74 and ≥ 75 years of age), study site and by low vs high risk of influenza complications (score < 50 vs ≥ 50).

Immunogenicity objective:

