8.2.3 Efficacy Data

Efficacy data will be analyzed using both the FAS (Efficacy) and the PPS, irrespective of the difference in size between the two analysis sets.

The following algorithm will be applied:

1. If less than 20% of subjects are without efficacy data (e.g., ILI swabs collected without any RT-PCR assessment record), then the analyses will be run on FAS and PPS and no further statistical evaluation will be performed.
2. If observations are missing for 20% or more of subjects, the missing mechanism will be analyzed with vaccine group as a categorical variable and a newly created variable describing the missing information as dependent variable (1=efficacy record present; 0=efficacy record not present). It will be tested, by chi-square test, if the proportion of missing observations/subjects varies significantly between vaccine groups. If the difference is significant with $P < 0.05$ then a sensitivity analysis will be performed of the primary efficacy analysis imputing randomly x% (from 0% to 100% in 10% increments) of missing data as PCR-confirmed cases.

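### The missing-outcome sensitivity analysis steps by 10 points; counted over all subjects and with similar missingness by arm, it skips the low range where the 40% margin is crossed

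*SAP*

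**What the plan says.** SAP 8.2.3 sets two conditions, and protocol 8.4.2.2.3 carries the same rule. The first concerns amount: "If observations are missing for 20% or more of subjects", the missing-data mechanism is examined by vaccine group with a chi-square test. The second concerns imbalance: "If the difference is significant with $P < 0.05$ then a sensitivity analysis will be performed of the primary efficacy analysis", done by "imputing randomly x% (from 0% to 100% in 10% increments) of missing data as PCR-confirmed cases".

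The only illustration of missing data is in the step for less than 20% missing, which speaks of subjects "without efficacy data (e.g., ILI swabs collected without any RT-PCR assessment record".

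The text does not state whether x is common to both arms, when an imputed case occurs, or what result would count as robust. The Efficacy FAS is itself limited to subjects who provide efficacy data (SAP 7.3), so it is also unclear which subjects are brought back for imputation.

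SAP 5 plans on a comparator attack rate of 3.5% at a one-sided alpha of 2.5%. For the vaccine arm its figures are "1.4% among the aQIV group, i.e. 60% assumed vaccine efficacy for aQIV, 238 events". The success margin for the primary objective is a lower confidence limit for VE above 40% (SAP 12.1).

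**The concern.** A sensitivity analysis of this kind should show how adverse the missing outcomes would have to be before the primary conclusion changes. The values of x that matter are those near the rate at which missing subjects could plausibly have had influenza. If missing data are counted over all subjects, the natural reference is the attack rate. Both planned rates lie between the first two grid points: 10/3.5 = 2.9 and 10/1.4 = 7.1.

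With one x for both arms, the imputed cases are also spread as if the vaccine had no effect in missing subjects. VE is pulled toward one minus the ratio of the arms' missingness, whatever the vaccine does. The risk is that the output reflects the missingness pattern more than the robustness of the result, and does so when the primary claim is under question.

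**Working it through.** **Inputs.** SAP 5 gives 4,860 evaluable per arm, attack rates of 3.5% and 1.4%, 238 events and a 40% margin. SAP 8.2.3 gives the 20% trigger and the grid. Assumptions: one x for both arms, and missing data counted over all subjects.

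**The plan's own figures.** Events: 4,860 × (0.035 + 0.014) = 238.1. Power: ln(0.6/0.4) × √(238/4) = 0.4055 × 7.714 = 3.128. Then Φ(3.128 − 1.960) = 87.9%, or Φ(3.128 − 2.000) = 87.0% at the final-stage alpha of 0.02275. The SAP gives 86.5%, so the inputs are consistent.

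**Formulas.** With m_A and m_C the proportions missing in the aQIV and comparator arms:

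- aQIV cases: a = 4,860 × [0.014(1 − m_A) + x·m_A]
- comparator cases: c = 4,860 × [0.035(1 − m_C) + x·m_C]
- VE = 1 − a/c
- lower limit = 1 − (a/c)·exp(1.96·√(1/a + 1/c))

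**Results at true VE 60%.**

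| Missing, aQIV / comparator | x | a / c | VE | Lower limit |
|---|---|---|---|---|
| 20% / 20% | 0% | 54.4 / 136.1 | 60% | 45% |
| 20% / 20% | 1.25% | 66.6 / 148.2 | 55% | 40% |
| 20% / 20% | 10% | 151.6 / 233.3 | 35% | 20% |
| 19% / 21% | 10% | 147.5 / 236.4 | 38% | 23% |
| 21% / 19% | 10% | 155.8 / 230.1 | 32% | 17% |
| 13% / 27% | 0% | 59.2 / 124.2 | 52% | 35% |
| 13% / 27% | 10% | 122.4 / 255.4 | 52% | 40.6% |

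*Small imbalance.* The 2-point difference is enough to trigger the analysis: z = 0.02/√(2 × 0.2 × 0.8/4,860) = 2.46, P = 0.014. In the 19%/21% row, 92.3 + 102.1 = 194.4 of 383.9 cases are imputed, or 51%.

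*Tipping point.* Equal missingness would not itself trigger the analysis; it is the centre of the two small imbalances. The tipping x there is about 1.3% with 4,860 per arm, 1.5% with the 5,346 randomized, and 1.8% with 6,075 (= 4,860/0.8, which leaves 238 observed cases). With 4,860 per arm and 19%/21% missing it is about 1.1% (a = 65.3, c = 145.6). With 21%/19% it is about 1.4% (a = 67.8, c = 150.5).

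*True VE needed at x = 10%.* With equal missingness the lower limit exceeds 40% only if true VE is about 87% (6,075 per arm) to 90% (4,860 per arm). The plan assumes 60%, and 65% for the key secondary.

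*Large comparator excess.* At 13%/27% the pull is toward 1 − 13/27 = 52%. The lower limit rises from 35% at x = 0% to 40.6% at x = 10%, so imputation turns a failing step into a passing one.

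*Scenarios the grid omits (20%/20%).* Each arm's missing subjects at that arm's planned rate: 68.0 / 170.1 cases, VE 60%, lower limit 47%. Both arms at the comparator rate: 88.5 / 170.1, VE 48%, lower limit 33%.

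**The case against.** A reader might infer that every non-zero step must fail at any plausible efficacy, so that the result is fixed in advance. The documents do not support that, for four reasons.

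1. The analysis runs only when missingness differs significantly between arms. A large comparator excess lets the 10% step pass at the planned VE, as the 13%/27% row shows.
2. The SAP does not say x is common to both arms. That is an inference from the absence of any arm-specific value.
3. The SAP attaches no pass or fail rule to this analysis. Judging it against 40% borrows the primary criterion, which is the only margin stated for that analysis.
4. The SAP's one example is a swab without an RT-PCR record, and swabs come from subjects who meet the ILI definition (protocol 3.5 and 7.2). For them the benchmark is PCR positivity, not the attack rate. The documents give no ILI rate. If 10% to 30% of each arm had an ILI, the planned rates imply positivity of 35% to 12% in the comparator arm and 14% to 5% in the aQIV arm. Suppose also that 20% of swabs were untested. With a 10% ILI rate, x = 10% adds 0.10 × 0.20 × 0.10 × 4,860 = 9.7 cases per arm, giving 64.2 / 145.8, VE 56% and lower limit 41%. With a 20% ILI rate the lower limit is 37%.

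These points stand and limit the conclusion. They do not remove it: the example is only an example, the trigger counts subjects, and the ambiguity itself needs resolving. It is also fair that the analysis may never run, since planned drop-out is 10%, and that it changes neither the primary estimate nor the success decision.

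**Conclusion.** The concern holds in a conditional form. If missing data are counted over all subjects, x is common to both arms and missingness is similar but just different enough to trigger the rule, the first non-zero step takes a VE of 60% to about 32% to 38% (lower limit 17% to 23%). The 40% margin is crossed below 2%, where the grid has no point other than zero. With a large comparator excess the same step can pass, because the common x drives VE toward the missingness ratio. Either way the grid gives little information on where the primary conclusion tips. If missing data means only untested swabs from ILI subjects, 10-point steps are less unreasonable, and the main gap is the undefined denominator. This is an inexpensive improvement to a conditional analysis, not a flaw in the primary analysis.

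**What to change.** In SAP 8.2.3, with protocol 8.4.2.2.3 aligned:

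- State what counts as missing efficacy data, over which denominator, and how an imputed case is given an event time for the Cox model.
- Let the imputed probability differ by arm.
- Use fine steps at the low end, for example 0% to 5% in 0.5-point steps. Keep coarser steps above that to cover PCR positivity among swabbed subjects.
- Include two named scenarios: each arm's missing subjects at that arm's observed rate, and both arms at the comparator's observed rate.
- Repeat the random draws and combine the log hazard ratios by Rubin's rules.
- Report the pairs of arm-specific probabilities at which the lower limit of VE crosses 40%.

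The cost is SAP wording, some programming and a larger output table, for an analysis that runs only if both triggers are met. No new data are needed and the primary analysis is unchanged.

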8.3 Multicenter Studies

Vaccine group effects will be investigated first using a linear model which allows for center differences, but does not consider vaccine-by-center interaction, i.e., the model only considers effects for center and vaccine. A center effect will be included in all analyses of the primary and secondary objectives.

To achieve a sufficient number of subjects for the statistical analysis, centers will be grouped according to a higher level factor, country. This factor will be used in the statistical models instead of center.

The analysis of vaccine group effect split by country will be provided in Section 14 of the CSR for the primary objectives. If significant vaccine effects are found in the trial, there will be an exploration of the heterogeneity of vaccine group effects across countries.

Results of vaccine by country interaction analysis will be provided in Appendix 16.1.9 of the CSR.

8.4 Multiple Comparisons and Multiplicity

The K-stage group-sequential design for efficacy introduces a multiple test problem. Therefore the familywise error rate (FWER) will be adjusted via an error-spending function ([Jennison and Turnbull 1999](#)) for each stage of the interim analyses that maintains the alpha for each interim analysis.

8.5 Immunogenicity Subsets

For the overall study - Approximately 10,620 subjects ≥ 65 years will be randomized to receive either aQIV or non-influenza comparator in a 1:1 allocation ratio, stratifying according to age (≥ 65 to 74 and ≥ 75), study site and comorbidity status (at risk/not at risk).

Within this randomization, a subset of 1702 subjects will be allocated for immunogenicity testing in a 4:1 ratio from either aQIV or non-influenza comparator, as described in [Section 4.1](#).

8.6 Subgroups

Unadjusted efficacy analysis will be performed by stratifying for the following subgroups:

- Age at enrollment categorized as 65-74, 75-84, and ≥ 85 years.
- Comorbidity/risk (yes/no) defined as assessment score < 50 or ≥ 50 based on scale described in the Section 5.1.2 of the protocol ([Hak, 2004](#));
- Previous influenza vaccination in the past 5 years (yes/no);
- Smoking status (yes/no);
- Sex;
- Race;
- Country;
- By season, if applicable.

If, in any subgroup, the number of confirmed ILI cases is < 10 then the statistical analysis in that subgroup will not be performed.

Unadjusted immunogenicity analysis will be performed by stratifying for the following subgroups:

- Age at enrollment categorized as 65-74, 75-84, and ≥ 85 years.
- Comorbidity/risk (yes/no) defined as assessment score < 50 or ≥ 50 based on scale described in the Section 5.1.2 of the protocol (Hak, 2004);
- Previous influenza vaccination in the past 5 years (yes/no);
- Sex;
- Race;

Safety analysis will be performed by stratifying for the following subgroups:

- Age at enrollment categorized as 65-74, 75-84, and ≥ 85 years.
- Sex;
- Race;
- Country

8.7 Data Transformation

Distributions of antibodies are generally skewed to the right and approximately log-normally distributed (Nauta, 2010). Therefore, prior to any statistical analysis that assumes normally distributed observations, antibody titers will be \log_{10} -transformed. GMTs and their 95% CIs will be then computed by exponentiating (base 10) the means and 95% CIs of the \log_{10} transformed titers.

8.8 Derived and Computed Variables

Demographics

In the case that Age and/or Body Mass Index must be recomputed by standard software

Age will be calculated in years using the following formula:

$$\text{Round} [(\text{Date of Visit 1} - \text{Date of Birth} + 1) / 365.25]$$

Body Mass Index (kg/m^2) will be calculated using the following formula:

$$\text{Mass (kg)} / \text{Height}^2 (\text{m}^2)$$

Immunogenicity

Values below the limit of quantification will be set to half that limit.

The rate of seroconversion is defined as the percentage of subjects with either a prevaccination HI titer < 1:10 and a postvaccination HI titer \geq 1:40 or a prevaccination HI titer \geq 1:10 and a \geq 4-fold increase in postvaccination HI titer.

Seroconversion is defined as binary variable for subjects with non-missing values pre-vaccination- and post-vaccination as:

= 1, if seroconverted (defined as the percentage of subjects with either a pre-vaccination HI titer < 1:10 and a post-vaccination HI titer \geq 1:40 or a pre-vaccination HI titer \geq 1:10 and a minimum 4-fold rise in post-vaccination HI antibody titer)

= 0, otherwise

Geometric Mean Titer

The GMT will be calculated using the following formula:

$$10^{\left\{ \frac{\sum_{i=1}^n \log_{10}(t_i)}{n} \right\}}$$

where t_1, t_2, \dots, t_n are n observed immunogenicity titers. The 95% confidence intervals for GMT will be calculated as $10^{\{M-t_{0.975, n-1}SE\}}$, $10^{\{M+t_{0.975, n-1}SE\}}$; where M and SE are the means and standard error of logarithm base 10 -transformed titers, respectively.

Geometric Mean Ratio

Geometric mean ratios (GMRs) measure the changes in immunogenicity titers *within* subjects.

The GMR will be calculated using the following formula:

$$10^{\left\{ \frac{\sum_{i=1}^n \log_{10} \left(\frac{v_{ij}}{v_{ik}} \right)}{n} \right\}} = 10^{\left\{ \frac{\sum_{i=1}^n \log_{10} (v_{ij}) - \log_{10} (v_{ik})}{n} \right\}}$$

where, for n subjects, v_{ij} and v_{ik} are observed immunogenicity titers for subject i at time-points j and k , $j \neq k$.

Duration in the Study

Duration in the study is defined in days as:

$$[\text{Last visit date (visit 15)}^a - \text{Enrollment date (visit 1)} + 1]$$

^aor premature discontinuation date (in case of withdrawal from the study)

The duration is missing if one of the dates is missing or incomplete.

Solicited Adverse Events

For details see [section 13.2](#).

Unsolicited Adverse Events

All adverse events will be characterized according to the date of occurrence related to the vaccination phase as follows:

- **Emergence before vaccination phase:** start date before the date of injection of study vaccine.
- **Emergence during vaccination phase:** start date on or after the date of injection of study vaccine or, adverse event increase in severity, including to “serious” adverse event.

If start date is equal to the first date of injection then “timing” variable (“On injection day, before injection”/“On injection day, after injection”) will be used to define whether the adverse event occur before or after the injection.

If an adverse event start date is missing or unknown, the adverse event will be considered as emergent.

When start and/or end dates of an adverse event are only partially known, adverse events will be categorized as emergent before, during, or after vaccination phase using the following rules:

- If the partial end date is before ($<$) the vaccination (i.e., year or year & month is/are before the study vaccination year or year & month) then the adverse event is emergent before vaccination phase.
- If the partial start date is equal or after (\geq) the first study vaccination (i.e., year or year & month is/are after or the same as the first study injection year or year & month) then the adverse event is emergent during vaccination phase.

The **maximum event severity** is the greatest severity associated with a preferred term (PT) for a reported adverse event according to the following order: Mild $<$ Moderate $<$ Severe. Unknown/ Missing severity is considered as severe (except for the definition of emergence).

Multiple AEs with the same PT for the same subject are counted only once.

Vaccination-related Adverse Events are those for which the cause has been evaluated by the investigator, and recorded as possibly related, probably related or unknown/missing.

Safety Laboratory Data

Not Applicable

Pre-study, Concomitant and Post-Vaccination Medications

A **previous medication** is a medication used only before the first study vaccination (i.e. medication end date $<$ first study vaccination date).

A **post-vaccination medication** is a medication used only after study vaccination date + 366 days / study termination date.

All other medications are **concomitant**.

When start and/or end dates of a medication intake are missing, the medication is considered as concomitant with the study vaccination schedule.

If the study vaccination date is missing then the medication is considered as concomitant with the study vaccination schedule, provided that the study vaccine was administered to the subject.

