5.1.3 Enrollment

After signing the ICF, if an individual is determined to be eligible for study participation, the investigator or delegate will enroll the subject and enter subject information and stratification information into the Interactive Response Technology (IRT) system.

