5.1.4 Randomization

Enroled subjects will be randomized in the IRT system by a 1:1 ratio to receive either aQIV or the non-influenza comparator vaccine Boostrix® and will be automatically assigned a unique Subject ID and Pack ID indicating the assigned treatment. The Subject ID will be the subject's unique identification number for all CRFs and associated study documentation that will be used for duration of the study. The Subject ID consists of a 7-digit number resulting from the combination of the site number, and the subject's order of randomization at the site. After randomization, the Screening Number ceases to be used and remains in the Screening and Enrolment Log only. The list of randomization assignments is produced by the IRT service provider and approved by Seqirus or delegate.

Randomization will be stratified by age (cohorts 65 to 74 years and 75 years and above), study site and also based on risk for complications from influenza (assessment score < 50 or ≥ 50).

If for any reason, after signing the ICF, the subject who is eligible and enroled fails to be randomized, this is called a randomization failure. Further guidance is provided in the CRF Instructions. The reason for all randomization failures should be recorded in the Screening and Enrolment Log and in the source document as specified in the Source Data Agreement (SDA). The information on subjects who are randomization failures should be kept distinct from subjects who are screen failures, as described in [Section 5.1.2, Screening](#).

If for any reason, after randomization the subject fails to undergo treatment, this is an Early Termination and the reason should be recorded in source document as specified in the SDA. The information on these Early Termination subjects should be kept distinct in the source documentation from randomization failures.

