8. GENERAL ISSUES FOR STATISTICAL ANALYSES

8.1 Adjustment for Covariates

The estimate of the hazard ratio and the respective estimate for relative vaccine efficacy (rVE) and pertaining 2-sided 95% confidence intervals will be calculated based on the Cox proportional hazards model with vaccine group as the main effect. Randomization stratifying factors (ie, by age (cohorts 65 to 74 years and 75 years and above), study site, and risk for complications from influenza (assessment score < 50 or ≥ 50) will be modelled as random effects as suggested by [Kahan and Morris \(2012\)](#). In case of computational difficulties due to small number of events (for example, in a subgroup analysis) an unadjusted hazard ratio will be estimated and reported. Small sites (<30 subjects) will be grouped within country.

The log-transformed antibody titer at day 1, Day 22, Day 181 and Day 366 will be analyzed, in key analyses, using an Analysis of Covariance (ANCOVA) model which includes the site effect (with small sites grouped within country), an effect defined by the log-transformed pre-vaccination antibody titer, age stratification and comorbidity (<50, ≥ 50). Summary tables will show both adjusted and unadjusted GMTs and adjusted and unadjusted ratios of GMTs for each vaccine group, except for subgroup analyzes which will present unadjusted estimates only.

Binary data tables will show unadjusted percentages.

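### If age is recomputed under SAP 8.8, the rounding formula moves subjects in the last half-year before 75 or 85 into the next age band

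*SAP*

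**What the plan says.** SAP 8.8 introduces its age derivation with a condition: "In the case that Age and/or Body Mass Index must be recomputed by standard software". It continues: "Age will be calculated in years using the following formula". In symbols, with V the Visit 1 date and B the birth date, the formula is Round[(V − B + 1)/365.25]. No rounding unit is stated.

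The age bands are set elsewhere:

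- SAP 8.6 gives "Age at enrollment categorized as 65-74, 75-84, and ≥ 85 years" for the efficacy, immunogenicity and safety subgroups. Protocol 8.3.6 uses the same bands.
- SAP 10.1 tabulates demographics by those three bands and by 65-74 versus 75 and over.
- SAP 8.1 puts the randomisation factors in the primary Cox model, including "by age (cohorts 65 to 74 years and 75 years and above". Protocol 8.4.2.2.3 writes the same split as under 75 versus 75 and over.

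At enrolment the site is to "enter subject information and stratification information into the Interactive Response Technology (IRT) system" (Protocol 5.1.3). Age is also collected as demographic data at screening (Protocol 5.1.2). SAP 4.1.1 analyses minor stratification errors in the corrected stratum in the FAS, PPS and Safety Set. Neither document says which age variable (collected, IRT or recomputed) defines the subgroups or a corrected stratum.

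**The concern.** The bands run 65-74, 75-84, 85 and over. They cover every subject without gaps only if age means age at last birthday, and the protocol's split at under 75 says the same thing for that cut. A formula that rounds to the nearest year does not respect these cuts. A subject aged 74.6 is under 75 but is returned as 75.

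In effect the labelled subgroups would become 65 to under 74.5, 74.5 to under 84.5, and 84.5 and over. The oldest band is where this could matter most. It is likely to be the smallest, and SAP 8.6 drops the efficacy analysis of any subgroup with fewer than 10 confirmed cases, so membership could decide whether that analysis is run.

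**Working it through.** The plan gives no figure to reproduce, so the check applies the formula to birth dates and compares the result with completed calendar years.

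**Inputs.** The formula is from SAP 8.8, read as rounding to whole years with halves up. The cuts at 75 and 85 are from SAP 8.6. N = 10,692 is from SAP 5. The example Visit 1 date, 15 October 2016, is an assumption.

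**Single cases.**

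- Born 15 April 1942: V − B + 1 = 27,213 days; 27,213/365.25 = 74.505, which rounds to 75. Completed age is 74, so the subject moves from 65-74 to 75-84.
- Born 10 April 1932: 30,870/365.25 = 84.518, which rounds to 85. Completed age is 84, so the subject moves from 75-84 to 85 and over.

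**Sweep of every birth date with completed age 65 to 94.** The formula misplaces 183 consecutive birth dates at the 75 cut (unrounded age 74.502 to 75.001) and 184 at the 85 cut (84.501 to 85.002). That is half a year of age at each cut. Taking the integer part but keeping the +1 and the 365.25 still misplaces one birth date at each cut, the day before the birthday. Completed calendar years misplaces none.

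**Number of subjects (illustrative).** Assume age density proportional to exp(−h(a − 65)) from 65 to 95, with h from 0 (flat) to 0.15 per year, and age recomputed for everyone.

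- Share crossing at 75: (e^(−9.5h) − e^(−10h)) / (1 − e^(−30h))
- Share crossing at 85: (e^(−19.5h) − e^(−20h)) / (1 − e^(−30h))
- For h = 0 both equal 0.5/30 = 1.67%.

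| h | Cross at 75 | Movers as share of derived 75-and-over group | Cross at 85 |
|---|---|---|---|
| 0 | 1.67% = 178 | 2.4% | 1.67% = 178 |
| 0.05 | 1.98% = 211 | 3.9% | 1.20% = 128 |
| 0.10 | 1.98% = 212 | 5.6% | 0.73% = 78 |
| 0.15 | 1.76% = 188 | 7.6% | 0.39% = 42 |

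The count at 75 is stable across these assumptions. The count at 85 is not, because it depends on how many very old subjects enrol.

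**The case against.** The strongest reply is that the formula may never be used. It is conditional on recomputation, and age is collected at screening. That is correct and limits the point to the fallback, but a pre-specified fallback should give the right answer when it is needed.

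It can also be said that no rounding unit is stated and that neither document uses the term completed years. Both are true. Whole years is the natural reading because the bands are in whole years. A finer unit would narrow the misplaced slice to half that unit below each cut without removing it.

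A reader might infer three stronger consequences that the documents do not support:

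- **Primary model.** SAP 8.1 uses the randomisation factors, and stratum information is entered in IRT by the site. Nothing says recomputed age replaces it. There is no stratum cut at 85, so subjects aged 84.5 to 85 cannot change model category at all.
- **False stratification errors.** SAP 4.1.1 defines incorrect stratification as randomisation on wrong baseline information. A rounded age produced later is not that. Correctly randomised 74-year-olds would be moved only if recomputed age drove the correction, which the SAP does not state.
- **Eligibility.** The formula would show someone aged 64.6 as 65, but the site decides eligibility at screening without it. Whether any deviation check uses it would depend on the deviation specification in SAP Appendix A, which was not available for this review.

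**Conclusion.** The formula is wrong as written for the bands it would feed, but the consequence is minor. If age is recomputed, subjects in the half-year before 75 or 85 are mislabelled in the age subgroups and demographic tables: about 178 to 212 of 10,692 at 75 and about 42 to 178 at 85. These counts rest on an assumed age distribution, on rounding to whole years, and on recomputing age for every subject. If recomputation were limited to some subjects, the numbers would fall in proportion.

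The error is a function of birth date and visit date, not vaccine group, so it does not by itself bias the comparison of the two vaccines. The age term of the primary model would be touched only if recomputed age replaced the IRT stratum or was used for the correction in SAP 4.1.1. The SAP leaves that open. Even then, the effect on the primary hazard ratio would be small.

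**What to change.** In SAP 8.8, replace the rounded formula with age in completed calendar years at Visit 1, that is, age at last birthday from the two calendar dates. Do not simply take the integer part of the present expression, since the +1 and the 365.25 still misplace the day before the birthday.

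Add one sentence saying that the model's age stratum is the IRT stratum, corrected only for genuine entry errors at baseline, and that the age subgroups and tables use completed-years age.

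The cost is two lines of SAP text and one line of derivation code, best settled before unblinding. No data collection, sample size or testing rule changes.
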